6.8 Safety Evaluation

Safety measures will include adverse event collection and C-SSRS administration at all visits, and medication side effect reporting collected by FIBSER and PRISE at Baseline (Day 0), Week 2, 4, 6 and 8 visits and at any unscheduled visits or during other contacts with the subject, as applicable.

7 ADVERSE EVENTS

7.1 Adverse Event (AE)

An AE is any untoward medical occurrence in a subject or clinical investigation subject administered a pharmaceutical product and which does not necessarily have to have a causal relationship with treatment (ICH, E2A). Adverse events will be assessed regardless of administration of a pharmaceutical product from time of informed consent signing until completion of study.

An AE can be any unfavorable and unintended sign (including an abnormal laboratory finding), symptom, or disease temporally associated with the use of a medicinal product, whether or not considered related to the medicinal product (ICH, E2A). Examples of AEs are as follows:

- Changes in the general condition of the subject.
- Subjective symptoms offered by or elicited from the subject.
- Objective signs observed by the investigator or other study personnel.
- All concurrent diseases that occur after the start of the study
- Any increase in severity or frequency of symptomatology of pre-existing diseases.
- Any clinically relevant abnormality in laboratory values, ECGs or physical findings that occurs during the study.

7.1.1 Documenting Adverse Events

At each visit, subjects are to be queried regarding any AEs that have occurred since the previous visit. Subjects will be asked to volunteer information concerning AEs with a non-leading question. Study site personnel will then record all pertinent information in the subject's eCRF.

At each study visit (and during any communication with a subject or subject representative occurring outside a defined study visit), all AEs reported by the subject or subject's representative or observed or otherwise identified by the treating investigator or other study personnel must be documented. Ongoing adverse events must be followed-up and updated in the eCRF, as appropriate, until the subject completes the study.

For every AE, the investigator must:

- Provide an assessment of the severity, causal relationship to psychotropic medication treatment, and seriousness of the event.
- Document all actions taken in regard to the AE.
- Detail any other treatment measures taken for the AE.

7.1.2 Assessing Severity

The treating investigator will provide an assessment of the severity of each AE by recording a severity rating on the appropriate AE reporting page of the subject's eCRF. *Severity*, which is a description of the intensity of manifestation of the AE, is distinct from *seriousness*, which implies a subject outcome or AE-required treatment measure associated with a threat to life or functionality. Severity will be assessed according to the following scale:

Mild: The AE was an annoyance to the subject but did not further hinder baseline

functioning; the AE may have been intermittent or continuous.

Moderate: The AE caused the subject to experience some discomfort or some interference with

normal activities but was not hazardous to health; prescription drug therapy may have

been employed to treat the AE.

Severe: The AE caused the subject to experience severe discomfort or severely limited or

prevented normal activities and represented a definite hazard to health; prescription

drug therapy and/or hospitalization may have been employed to treat the AE.

7.2 Serious Adverse Event (SAE)

An SAE is any untoward medical occurrence that is/causes: (ICH, E2A):

- Life-threatening
- Death

- Inpatient hospitalization or prolongation of existing hospitalization
- Persistent or significant disability/incapacity
- Congenital anomaly/birth defect
- Important medical events that may not result in death, be life-threatening, or require hospitalization may be considered serious when, based on appropriate medical judgment, they may jeopardize the subject and may require medical or surgical intervention to prevent one of the outcomes listed in this definition. Examples of such medical events include allergic bronchospasm requiring intensive treatment in an emergency room or at home, blood dyscrasias or seizures that do not result in inpatient hospitalization, or the development of drug dependency or drug abuse. However, emergency room visits that do not result in admission to the hospital should be evaluated for one of the other serious outcomes (e.g., life-threatening, other serious [medically important] event).
- Pre-planned surgeries or procedures for pre-existing, known medical conditions for which a patient requires hospitalization are not reportable as serious adverse events. This should be clearly documented in the subject's source document.

7.2.1 Reporting Requirements for Serious Adverse Events

Serious adverse events (SAEs) should be reported to Genomind no later than 48 hours after learning of the event. Genomind should be notified by email using the serious adverse event form. The designated email contact information can be found on the serious adverse event form cover page. All subjects with a serious adverse event must be followed-up and the outcomes reported to the sponsor. The investigator must supply Genomind with any additional requested information. All relevant data and updates will be documented on the appropriate eCRF pages.

7.2.2 Reporting to the IRB

The investigator should promptly report to his/her Institutional Review Board (IRB) all SAEs per governing IRB requirements.

7.3 Pregnancy

Study personnel must report the occurrence of a pregnancy to the sponsor. A pregnancy is not considered an AE or SAE unless complications associated therewith qualify the event as such.

7.4 Investigator Alert Notification

Genomind or its designee will promptly inform all investigators participating in this clinical trial of any new safety information that may be relevant to the utilization of the Genecept Assay TM results.

7.5 General Safety Monitoring

Genomind will meet periodically as deemed appropriate to review safety data. These data will include but are not limited to:

AEs that result in an early study withdrawal

SAEs

Appropriate action, if needed, will be taken based upon this review and in consultation with the clinical team.

8 STATISTICAL CONSIDERATIONS

8.1 General

Note: The Statistical Considerations which follow generally apply to the Main Study analysis and also the add-on Exploratory Elderly MDD Study analysis. Important exceptions will be noted in the text below. A SAP for the Exploratory Elderly MDD Study, incorporated in the overall SAP (V 3.0), will fully detail the statistical approaches. The SAP (V 3.0) will be finalized, signed, and approved by the Sponsor before the Elderly MDD Study is unblinded.

Summarizations will be provided in tables and figures. Safety and efficacy variables will be summarized by visit using descriptive statistics. For continuous variables, this will include the number of non-missing values, mean, standard deviation (SD) or standard error of the mean, median, minimum, and maximum. Categorical variables will be summarized using counts and percentages.

Unless otherwise stated, the significance level for statistical tests will be two-sided, alpha=0.05, with no adjustment for multiple comparisons

The statistical analysis plans (SAPs) for the Main Study and Exploratory Elderly MDD Study will document the technical details of statistical methods, supplementing the key analysis details in this protocol. The Main Study SAP will be finalized (V 2.0), signed, and approved by the Sponsor before the first subject is randomized. If necessary, during the study and before unblinding the Main Study database this SAP may be amended using the same approval process. SAP amendments will clearly document and justify changes, and be completed as early as possible, and in any case prior to unblinding the study database. Revisions in statistical approaches after unblinding (such as performing sensitivity analyses suggested by the data) will be discussed in the CSR Statistical Methods section.

Pooled Investigative Sites: For all statistical analyses, sites with few subjects (< 7 subjects) will be pooled into larger "sites" based on number enrolled. "Investigative site" in all statistical analyses will refer to "sites" as pooled. Details of the pooling algorithm will be in the SAP. Note: the pooling algorithm will be applied separately to the Main Study and the Exploratory Elderly MDD Study.

Missing data: As underscored in Sections 9.4.2 and 9.8, reducing the level of missing data in this trial will allow more interpretable and powerful efficacy analyses, and maximize the sensitivity of the trial with the given sample size. Over recent years there has been growing awareness of the impact of missing data, with resulting improvement of statistical approaches to handling missing data³⁷⁻⁴⁰. However, it has also become apparent that statistical analyses can patch but not solve the loss of interpretability and credibility from missing data⁴¹. Most crucial is to first reduce missing data as much as possible. This has spurred development of straightforward changes in trial conduct with potential to

dramatically reduce the dropout rate⁴²⁻⁴⁴. The influential report of the 2010 National Research Council Missing Data Panel⁴⁵, superbly summarized expert consensus on handling missing data, including measures to reduce dropouts and missing data:

- 1) Select investigators who have a good track record with respect to enrolling and following participants and collecting complete data in previous trials.
- 2) Set acceptable target rates for missing data and monitor the progress of the trial with respect to these targets.
- 3) Provide monetary and nonmonetary incentives to investigators and participants for completeness of data collection, as long as they meet rigorous ethical requirements.
- 4) Limit the burden and inconvenience of data collection on the participants, and make the study experience as positive as possible.
- 5) Train investigators and study staff that keeping participants in the trial until the end is important, regardless of whether they continue to receive the assigned treatment. Convey this information to study participants.
- 6) Collect information from participants regarding the likelihood that they will drop out, and use this information to attempt to reduce the incidence of dropout.
- 7) Keep contact information for participants up to date.

These recommendations have been endorsed by clinical trialists, editorial staff of major medical journals, and regulatory agencies⁴⁶⁻⁴⁸. Trials managed consistent with the NRC recommendations have indeed shown important reduction in dropout rate.

This trial will incorporate as many of these recommendations as possible. All analyses will be implemented using SAS software, version 9.3 or later.

8.2 Efficacy Analysis Estimands

This trial is a comparison of outcomes between two treatment strategies, evaluated at 8 weeks. For practical interpretation, this implies the statistical analyses should estimate and test the difference in Week 8 outcomes for all subjects, irrespective of attrition or compliance. [This may also be described as following the Intent to Treat (ITT) principle, but there is confusion about the use of this term when there is missing data, and ITT terminology will not be used further here.]. Specifying the "estimands") (what is being estimated), aligned with the study purpose, is the basis for the formal statistical methods which follow.

8.2.1 Primary Efficacy: AGT vs TAU

-Difference at Week 8 in SIGH-D-17 mean change from baseline, for all randomized subjects.

8.2.1 Secondary Efficacy: AGT vs TAU

- -Difference at Week 8 in QIDS-SR16 mean change from baseline, for all randomized subjects.
- -Difference at Week 8 in mean % improvement from baseline in SIGH-D-17 scores, for all randomized subjects.

Page 32 v26-May-17

- -Difference at Week 8 in mean % improvement from baseline in QIDS-SR16 scores, for all randomized subjects.
- -Difference in % treatment responders at Week 8, for all randomized subjects. Treatment response will be defined in 3 different ways:
- ≥ 50% reduction of SIGH-D-17 from baseline for blinded rater assessment
- ≥ 50% reduction of QIDS-SR16 from baseline for subject-rated assessment

Score of < 3 on the CGI-I from baseline for the unblinded clinician assessment

-Difference in % treatment remitters at Week 8, for all randomized subjects. Remission is defined for the SIGH-D-17 and the QIDS-SR16:

Score of < 7 on the SIGH-D-17 from baseline for blinded rater assessment

Score of \leq 5 on the QIDS-SR16 from baseline for subject-rated assessment.

-Difference at Week 8 in Clinical Global Impression – Improvement (CGI-I), % scores, for all randomized subjects.

8.3 Safety Endpoints

Treatment Emergent Adverse Events (TEAEs)

Frequency and severity of medication-induced side effects based on collection of FIBSER, PRISE and Adverse Events

-Columbia-Suicide Severity Rating Scale (C-SSRS) Outcomes

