	-To assess the percentage of responders at Week 8, based on SIGH-D-17, QIDS-SR16, and Clinical Global Impression—Improvement (CGI-I), respectively. Treatment response will be defined in 3 different ways: Blinded Rater Assessment: ≥ 50% reduction from baseline of SIGH-D-17 score; Subject-Rated Assessment: ≥ 50% reduction from baseline of QIDS-SR16; Unblinded Clinician Assessment: ≤ 3 score on the CGI-I; -To assess the percentage of remitters at Week 8, based on the SIGH-D-17 and QIDS-SR16, respectively. Remission is defined for the SIGH-D-17 and the QIDS-SR16: Blinded Rater Assessment: ≤ 7 score on the SIGH-D-17; Subject-Rated Assessment: ≤ 5 score on the QIDS-SR16 -To assess the impact of the Genecept Assay TM on adverse events, based on Frequency, Intensity and Burden of Side Effects Rating (FIBSER) and Patient-Related Inventory of Side Effects (PRISE), frequency and severity of adverse events and Columbia-Suicide Severity Rating Scale (C-SSRS) outcomes.				
Objective of Exploratory Elderly MDD Study	To perform an exploratory, add-on study, in elderly subjects age 65 years and older, to assess the efficacy and safety of AGT vs TAU in Major Depressive Disorder. Primary efficacy will be measured by change in Hamilton Depression Rating Scale (SIGH-D-17) at 8 weeks.				
	This study will provide additional data on this important, Medicare-eligible population, which is sparsely represented in the Main Study ($<$ 8% of subjects). As specified in Protocol Amendment 2, after the Main Study enrollment finishes, 70 subjects, age \ge 65, will be randomized to the add-on study. Except for change in age of inclusion, all study procedures will be identical to the Main Study.				

Study Design	In this randomized clinical trial, subjects will be assigned to either an assay-guided treatment condition (AGT) or a treatment-as-usual condition (TAU). All subjects will provide a DNA sample at the Screening Visit for the Genecept Assay TM . In the AGT condition, assay results will be provided to the treating investigator, who will use the results to guide antidepressant pharmacotherapy. In the TAU condition, the investigator will treat the subjects without the knowledge of the pharmacogenetic testing results. Assay results for all subjects will be provided to the investigator once all Week 8 visit procedures have been completed. Raters of the primary endpoint assessment and subjects will remain blinded to treatment assignment.

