9.4.4 Analyses of Key Secondary Efficacy Variables

The test for the following secondary continuous variables will use the same MMRM model in the FAS population, outlined for the primary analysis:

- Difference at Week 8 in QIDS-SR16 mean change from baseline.
- Difference at Week 8 in mean % improvement from baseline in SIGH-D-17 scores.
- Difference at Week 8 in mean % improvement from baseline in QIDS-SR16 scores.
- Difference at Week 8 in mean change of CGI-S.

Note: For the Exploratory Elderly MDD Study, the QIDS-SR16 mean change from baseline will be tested and summarized using the ANCOVA methodology described for the primary analysis. The remaining secondary efficacy variables will be descriptively summarized.

The Mantel-Haenszel method, stratified by investigative site, in the FAS population, will test AGT vs TAU estimates based on categorical variables:

- Difference in % treatment responders at Week 8, done separately for SIGH-D-17, QIDS-SR16 and CGI-I. Treatment response is defined as ≥ 50% reduction of SIGH-D-17 from baseline to Week 8 for blinded rater assessment, ≥ 50% reduction of QIDS-SR16 from baseline to Week 8 for subject-

Page 37 v26-May-17

rated assessment, score of \leq 3 on the CGI-I from baseline to Week 8 for the unblinded clinician assessment. If Treatment Response is missing at Week 8, the subject will be considered a Week 8 treatment non-responder. The two-sided p-value, estimated odds ratio and 95% CI for the odds ratio will be computed.

- Difference in % treatment remitters, done separately for SIGH-D-17 and QIDS-SR16, at Week 8. Remission is defined as score of ≤ 7 on the SIGH-D-17 from baseline to Week 8 for blinded rater assessment, score of ≤ 5 on the QIDS-SR16 from baseline to Week 8 for subject-rated assessment. If Treatment Remission is missing at Week 8, the subject will considered a Week 8 treatment non-responder. The two-sided p-value, estimated odds ratio and 95% CI for the odds ratio will be computed
- Difference at Week 8 in Clinical Global Impression Improvement (CGI-I)

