#### Analyses of Key Secondary Efficacy Variables

The test for the following secondary estimates based on continuous variables will use the MMRM model in the FAS population, as described for the primary analysis:

- Difference at Week 8 in QIDS-SR16 mean change from baseline.
- Difference at Week 8 in mean % improvement from baseline in SIGH-D-17 scores.
- Difference at Week 8 in mean % improvement from baseline in QIDS-SR16 scores.

- Difference at Week 8 in mean change from baseline of CGI-S.

The Mantel-Haenszel method, stratified by investigative site, in the FAS population, will test AGT vs TAU estimates based on categorical variables:

- Difference in % treatment responders at Week 8, done separately for SIGH-D-17, QIDS-SR16 and CGI-I. Treatment response is defined as  $\geq 50\%$  reduction of SIGH-D-17 from baseline to Week 8 for blinded rater assessment,  $\geq 50\%$  reduction of QIDS-SR16 from baseline to Week 8 for subject-rated assessment, score of  $\leq 3$  on the CGI-I from baseline to Week 8 for the unblinded clinician assessment. If Treatment Response is missing at Week 8, the subject will be considered a Week 8 treatment non-responder. The two-sided p-value, estimated odds ratio and 95% CI for the odds ratio will be computed.
- Difference in % treatment remitters, done separately for SIGH-D-17 and QIDS-SR16, at Week 8. Remission is defined as score of ≤ 7 on the SIGH-D-17 from baseline to Week 8 for blinded rater assessment, score of ≤ 5 on the QIDS-SR16 from baseline to Week 8 for subject-rated assessment. If Treatment Remission is missing at Week 8, the subject will considered a Week 8 treatment non-responder. The two-sided p-value, estimated odds ratio and 95% CI for the odds ratio will be computed
- Difference at Week 8 in CGI-I profile.

#### 

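### Do the strict signs in Protocol 8.2.1 (CGI-I below 3, SIGH-D-17 below 7) leave the responder and remitter endpoints undefined, and is an extra CGI-I analysis at scores 1-2 needed?

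*Protocol*

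**What the plan says.** Protocol 8.2.1 (Secondary Efficacy) lists the responder and remitter estimands. CGI-I response reads "Score of < 3 on the CGI-I from baseline for the unblinded clinician assessment" and SIGH-D-17 remission reads "Score of < 7 on the SIGH-D-17 from baseline for blinded rater assessment". In the same list, QIDS-SR16 remission carries a non-strict sign before "5 on the QIDS-SR16 from baseline for subject-rated assessment". Protocol 8.2 introduces the estimands by saying that specifying them "is the basis for the formal statistical methods which follow".

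Elsewhere the signs are non-strict. The Secondary Objectives in the Protocol summary give "Unblinded Clinician Assessment: ≤ 3 score on the CGI-I". Protocol 9.4.4, which specifies the tests, states "Remission is defined as score of ≤ 7 on the SIGH-D-17 from baseline to Week 8 for blinded rater assessment" and also uses ≤ 3 for CGI-I response. SAP 1.3, SAP 2.1 and SAP 3.4 (Main Study and Exploratory Elderly MDD Study) all use ≤ 3 and ≤ 7.

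On method, SAP 3.4 says "The Mantel-Haenszel method, stratified by investigative site, in the FAS population, will test AGT vs TAU estimates based on categorical variables". Each responder and remitter comparison gets a p-value, an odds ratio and a 95% CI. Missing outcomes count as failures: "If Treatment Response is missing at Week 8, the subject will be considered a Week 8 treatment non-responder". The same SAP list also includes a Week 8 comparison of the CGI-I profile, and both estimand lists include CGI-I % scores at Week 8.

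**The concern.** CGI-I takes whole values from 1 to 7, so below 3 means scores 1-2 and ≤ 3 means scores 1-3. Likewise, below 7 on the SIGH-D-17 excludes a patient who scores exactly 7. Because Protocol 8.2 presents the estimands as the foundation for the methods, a reader who starts there counts fewer responders and remitters than one who starts from Protocol 9.4.4 or the SAP. A choice between two definitions after unblinding would be undesirable.

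A second worry attaches to CGI-I. The rating comes from the unblinded treating side, and ≤ 3 appears to count any improvement as response. That looks like a lower bar than the 50% reductions required on the other two scales. The plan gives no odds ratio at scores 1-2, which is what the strict sign would mean. One could therefore ask for that odds ratio as a supportive row, so that the result is visible under either reading.

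**Working it through.** **1. The definitions side by side**

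| Place | CGI-I response | SIGH-D-17 remission |
|---|---|---|
| Protocol summary, Secondary Objectives | ≤ 3 | ≤ 7 |
| Protocol 8.2.1 (estimand list) | < 3 | < 7 |
| Protocol 9.4.4 (analysis) | ≤ 3 | ≤ 7 |
| SAP 1.3 | ≤ 3 | ≤ 7 |
| SAP 2.1 (estimand list) | ≤ 3 | ≤ 7 |
| SAP 3.4, Main Study | ≤ 3 | ≤ 7 |
| SAP 3.4, Elderly Study | ≤ 3 | ≤ 7 |

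One place out of seven differs. SAP 2.1 is the counterpart of that place: it repeats the response and remission definitions in nearly the same words, with ≤. QIDS-SR16 remission is ≤ 5 throughout.

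**2. Does either threshold enter the sample size?** No. The plan's figure rests on the continuous primary endpoint (difference 3.1, SD 7.2, two-sided 0.05, power 90%):

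- Normal approximation: n = 2 × (1.960 + 1.282)² × (7.2/3.1)² = 2 × 10.51 × 5.394 ≈ 113.4, so 114 per group.
- The exact t calculation gives 115, as printed.
- Dropout: 115/0.77 = 149.4, so 150 per group and 300 in total, as printed.

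**3. How much would the wrong sign change?**

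*CGI-I.* The only frequencies in the documents are in Protocol 1.3: 87% improved and 62% much or very much improved. If these are read as scores 1-3 and 1-2, about 87 − 62 = 25 points sit at score 3. With missing counted as non-response:

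- 10% missing: 25 × 0.90 = 22.5 points, about 68 of 300.
- 23% missing: 25 × 0.77 = 19.25 points, about 58 of 300.

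*SIGH-D-17.* The documents give no Week 8 distribution. Assume a normal distribution truncated at the bottom of the scale, a Week 8 mean of 10 to 16 and an SD of 6.12 or 7.2. The mass between 6.5 and 7.5 then runs from 2.2% (mean 16, SD 6.12) to 6.0% (mean 10, SD 6.12). Of 300 × 0.90 = 270 completers, that is 6 to 16 patients.

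So the sign would matter if it were programmed. Step 1 shows that the analysis text does not call for it.

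**4. Would an odds ratio at scores 1-2 add information reliably?** Take 150 per arm and 10% missing. Set the AGT completer rate to Φ(Φ⁻¹(p) + d), where p is the TAU completer rate. Multiply both rates by 0.90 and use the unpooled standard error with a two-sided 0.05 test. Hold the gap between the cut-offs at 25 points and take d = 0.43, the plan's own effect size.

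| TAU completers at 1-2 / at 1-3 | Power at 1-2 | Power at ≤ 3 |
|---|---|---|
| 62% / 87% | 68% | 29% |
| 25% / 50% | 76% | 75% |
| 15% / 40% | 69% | 77% |

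First row in full: AGT completers are 76.9% and 94.0%. At scores 1-2 the compared rates are 0.558 and 0.692, with standard error 0.055, so power is Φ(0.134/0.055 − 1.96), about 68%. At ≤ 3 the rates are 0.783 and 0.846, with standard error 0.045, which gives about 29%.

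The ordering reverses with the assumed TAU rate, and the documents do not fix that rate. Precision is similar. The 95% CI factor, exp(1.96 × √(2/(nP(1 − P)))) with n = 150, is 1.58 to 1.94 at scores 1-2 and 1.57 to 1.73 at ≤ 3. Neither cut-off is generally better.

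**The case for a change.** The case for acting has real content. The mismatch is there in the text, in a section the protocol treats as foundational. Conversion damage is not proven: the ≥ signs and the ≤ 5 in the same list came through. The two CGI-I cut-offs can also disagree. If AGT had 50% at scores 1-2 and 25% at score 3, against 40% and 35% under TAU, the odds ratio would be (0.5/0.5)/(0.4/0.6) = 1.5 at scores 1-2 and 1.0 at ≤ 3. The cost would be two signs and one table row.

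What stands is the clerical point. If the signs are genuine, Protocol 8.2.1 has two slips. The surviving ≤ 5 is weak evidence that they are. In the converted text the inequality signs are rendered in mixed styles within this list and again within 9.4.4, so one correct sign says little about its neighbours.

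The request for an extra row does not stand. The ≤ 3 cut-off is prespecified in every analysis section, and the summary and SAP 1.3 openly label it as an unblinded assessment. Apart from the disputed sign, no document treats scores 1-2 as response. A pattern such as the one in the example should be visible in the CGI-I profile. Aligning 8.2.1 with the rest also removes the second reading that the row was meant to cover, and the row would do nothing for SIGH-D-17 remission. It would add one more unadjusted comparison on an unblinded rating.

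**Conclusion.** No change to the analysis plan follows. At most this is a clerical slip in one list, and it may be only a conversion fault; comparing two signs with the source protocol settles which. In either case Protocol 9.4.4 and the SAP lead to one set of responder and remitter counts, so no planned result, power figure or conclusion moves, and the 300-subject sample size is untouched.

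The figures of up to 25 points (CGI-I) and 2.2% to 6.0% (SIGH-D-17) show what is at stake only if an analyst used 8.2.1 against every other definition. The first rests on an uncontrolled, unblinded, mixed-diagnosis study and on scale anchors the protocol does not print between the two ends. Its counts of 300 are randomized subjects, whereas the analysis uses the FAS. The second rests on assumed Week 8 means and a normal shape.

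The extra odds ratio at CGI-I scores 1-2 is a preference without a demonstrated gain. This assumes that the planned CGI-I profile and % scores are reported as percentages by score and arm, as their names suggest.
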